6.10 Study Medication Exposure and Compliance

Duration of exposure is defined as the total number of days a subject is exposed to any study treatment. This will be calculated for each subject by taking the difference between the date of last dose minus the date of the first dose, plus 1 (date of last dose minus date of first dose +1).

Treatment duration will be categorized in days as: Day 1 to \leq Day 9, Day 10 to \leq Day 16, Day 17 to \leq Day 23, Day 24 to \leq Day 30, Day 31 to \leq Day 37, Day 38 to \leq Day 44, Day 45 to \leq Day 51, Day 52 to \leq Day 58 and \geq Day 59. The number and percentage of subjects in each duration group will be summarized by treatment group for the Safety population.

Duration of Treatment exposure will also be summarized using descriptive statistics (n, mean, SD, median, minimum, and maximum).

Percent of study drug compliance is defined as $\{(number\ of\ capsules\ dispensed\ minus\ number\ of\ capsules\ returned) / [4 * (date\ of\ last\ dose\ minus\ date\ of\ first\ dose\ +\ 1)]\} * 100\%$. If for a certain period no capsules are returned, the data is considered missing and not accounted for, and therefore this period will also not be accounted for in the denominator (=number of planned doses).

For each treatment, SM compliance will be summarized by compliance category (<80%, 80-120%, and >120%) using number and percent of subjects in each compliance category for the safety population. Study medication compliance will also be summarized as a continuous variable using descriptive statistics (n, mean, standard deviation, median, minimum, and maximum) for each treatment.

The summary of duration of exposure to study medication and compliance will be presented for each treatment period (Titration period, Maintenance period, and combined Titration and Maintenance period) in Table 14.1.2.5 and Listings 16.2.5.1.1 - 16.2.5.1.3.

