6.3.4 Per-Protocol (PP) population

The Per Protocol (PP) population consists of all subjects in the ITT population who have completed all 10 visits with no missing ADHD-RS-5 assessments and no major protocol violations. Subjects will be analyzed according to the treatment they received.

The analysis population will be indicated as a subtitle in each table, listing and figure.

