6.5 Protocol Deviations

The date of and reason for protocol deviations will be documented in all cases. Major protocol deviations will include the following but not limited to:

- 1) Subjects enrolled in the study but did not meet the inclusion/exclusion criteria.
- 2) Subjects who missed doses as per the treatment he was randomized to.
- 3) Subjects who received non-randomized medication.
- 4) Subject's treatment compliance < 80% or > 120%.

Major protocol violations will be finalized before the database lock and will be added to the above list.

Protocol violations will be summarized in Table 14.1.1.4.

Subjects with major protocol deviations will be listed based on all randomized subjects. The listing will include a brief description of the deviation, deviation category, and if applicable, study day when deviation occurred along with other pertinent information (Listing 16.2.2.3).

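### The compliance rule in SAP 6.10 treats a genuine return count of zero as missing, which can bias the compliance summary downward and make the 80%/120% deviation flag wrong

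*SAP*

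**What the plan says.** Section 6.10 of the SAP introduces its formula with "Percent of study drug compliance is defined as". The numerator is capsules dispensed minus capsules returned. The denominator is four capsules for each day from first to last dose.

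It then gives the rule at issue: "If for a certain period no capsules are returned, the data is considered missing and not accounted for". The same sentence drops that period's planned capsules from the divisor, so a period with no return is removed from both parts of the ratio.

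The result is used in two places:

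- In section 6.10, for the safety population: "SM compliance will be summarized by compliance category (<80%, 80-120%, and >120" per cent. A continuous summary is given as well (Table 14.1.2.5).
- In section 6.5, as the fourth listed major deviation: "Subject's treatment compliance < 80% or > 120" per cent. The second listed item is separate: "Subjects who missed doses as per the treatment he was randomized to".

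Section 6.3.4 limits the per-protocol (PP) set to ITT subjects "who have completed all 10 visits with no missing ADHD-RS-5 assessments and no major protocol violations". The SAP uses that set for supplementary analyses only.

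**The concern.** In the SAP's own formula, a returned count of zero is a valid value: the whole supply for the period was used. The rule gives it the same treatment as a container that never came back, where the count really is unknown. Nothing in the text tells a programmer to handle the two differently.

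Whether a period is deleted therefore depends on the quantity being measured. When zeros are real, the deleted periods are those with the highest recorded use, and compliance is estimated only from periods with capsules left over. Three results are at stake:

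- the compliance table, which would be shifted downward;
- subjects with zero return in every period, who would have no value;
- the <80%/>120% flag, which could be raised wrongly at the lower limit or missed at the upper one.

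**Working it through.** The SAP contains no worked compliance figure to reproduce, so the check applies its formula with and without the deletion rule.

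**Inputs from the SAP.** Four planned capsules per day (6.10). Limits of 80% and 120% (6.5, 6.10). Drug return and compliance checked at Visits 3 to 10, about weekly, with a window of ±2 days (Table 1).

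**Assumptions.** A period is one week, so there are 8 periods of 4 × 7 = 28 planned capsules, 224 in total. The SAP does not give the quantity dispensed per period. It is varied: 28 (exact supply), 32 (one spare day) and 36 (two spare days).

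**Formulas.** For period *i*, let D be dispensed, R returned and P planned.

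- All periods kept: 100 × Σ(D − R) / ΣP.
- SAP rule: the same sums, over periods with R > 0 only.

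Let *k* be the number of weeks with a real zero return.

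**1. Exact supply (28), other weeks at 21 of 28.** With all periods kept, compliance is (28k + 21(8 − k)) / 224. Under the rule it is 21/28 = 75.0% for every k from 0 to 7.

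| k | All periods kept | SAP rule |
|---|---|---|
| 1 | 175/224 = 78.1% | 75.0% |
| 2 | 182/224 = 81.3% | 75.0% |
| 4 | 196/224 = 87.5% | 75.0% |
| 7 | 217/224 = 96.9% | 75.0% |
| 8 | 224/224 = 100% | 0/0, no value |

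From k = 2 on, the <80% flag is wrong.

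**2. One spare day (32), other weeks at 28 of 28.** With all periods kept, compliance is (224 + 4k) / 224. This runs from 228/224 = 101.8% (k = 1) to 252/224 = 112.5% (k = 7), against 100.0% under the rule. No category changes. At k = 8 it is 256/224 = 114.3%, against no value.

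**3. Two spare days (36), other weeks at 28 of 28.** With all periods kept, compliance is (224 + 8k) / 224.

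- k = 5: 264/224 = 117.9%, against 100.0%. Same category.
- k = 6: 272/224 = 121.4%, against 100.0%. The >120% flag is missed.
- k = 7: 280/224 = 125.0%, against 100.0%. Flag missed.
- k = 8: 288/224 = 128.6%, against no value. Flag missed.

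**4. Limit on the direction of bias.** Steps 1 to 3 use equal supply and equal period length. Under those conditions a zero-return week has the highest ratio, so deleting it can only lower compliance or leave it unchanged. A late visit can break this. With 36 dispensed over 9 days, full compliance uses 4 × 9 = 36, so a zero return is exactly 100%. With 28 dispensed over 9 days, a zero return is 28/36 = 77.8%, and deleting that period could raise the subject's figure.

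**The case against.** **The authors may have meant only containers not brought back.** Calling the data missing fits absent accountability records, and for those, removing the period from numerator and denominator is reasonable. This stands as a plausible intention. The text does not say it, and a literal reading deletes real zeros too.

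**The size depends on a quantity the SAP does not give.** This stands. With a ±2 day window, some spare supply is plausible. A compliant subject seen on schedule would then return capsules and keep the period. One spare day changes no category in the example, and two spare days do so only in an extreme pattern. What a period means is also not defined, since the same section reports by titration, maintenance and both combined.

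**A reader might infer that the rule expels well-compliant subjects from the PP set.** The SAP does not support this. Section 6.5 lists missed doses as a major deviation in its own right. Under exact supply, anyone the rule pushes below 80% has left-over capsules and so has missed doses. Read literally, the subject at 96.9% is excluded whatever the compliance figure. The subject with 0/0 has no value below 80% or above 120%, so the compliance flag is not raised and does not exclude that subject. The missed-dose item has no threshold, and if any single missed dose counted, the <80% limit beside it would add little. It is therefore fair to say only that wrong <80% flags may not change PP membership.

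**A reader might also infer that, with spare supply, every deleted period hides over-use.** The late-visit case in step 4 of the working shows otherwise.

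**Conclusion.** The point holds as a defect in a stated rule with limited reach. Section 6.10 does not separate a recorded zero from an unknown count. Where the zero is real, and supply and period length are equal, compliance is biased downward and a subject with zero return throughout has no value.

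Under exact supply with other weeks at 75%, the <80% flag is wrong from two full-use weeks on, and the understatement reaches 96.9 − 75.0 = 21.9 percentage points at seven. With other weeks at 100%, one spare day changes no category, and two spare days hide use above 120% only when at least 6 of 8 weeks have zero return. These sizes rest on assumed dispensing quantities and weekly periods.

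The effect falls on the compliance table and the section 6.5 flag. The possible effect on the PP set is mainly undetected use above 120%, and only supplementary analyses use that set. The primary and key secondary ITT analyses are not affected. The point should be corrected, but it does not threaten the trial's main conclusions.

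**What to change.** Reword the rule in section 6.10 so that a period is missing only when the container was not returned or the count was not recorded. When the container comes back empty, enter a returned count of 0 and keep the period in numerator and denominator. State in the same place what a period is (for example, the interval between consecutive dispensing and return visits).

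The cost is a sentence or two of SAP text and a matching line in the dataset specification, provided the drug-accountability eCRF records return status. If the eCRF cannot tell the two cases apart, say so in the SAP and report compliance, with the <80%/>120% categories, under both assumptions: all zero returns taken as real, and all taken as missing. Settle this before the major deviations are finalized for database lock.

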3.2 Schedule of Visits and Procedures Study

All subjects who are randomized and take any SM will be followed according to the protocol regardless of the number of doses of SM taken, unless consent for follow-up is withdrawn. [Table 1](#) below presents the Schedule of Visits and Procedures for the study.

Table 1: Schedule of Visits and Procedure

Period	Screening	Treatment Phase			
		Titration		Maintenance	
		Baseline, Randomization			End of Study ⁱ
Visit Number	1	2	3, 4	5-9	10
Visit Day		1	7, 14	21, 28, 35, 42, 49	56
Visit Window (days)	≤28d before V2		±2	±2	±2
Informed Consent/Accent (if applicable) ^a	X				
Medical and Psychiatric History	X				
Mini-KID	X				
Demographics	X				
Urine Drug Screen	X				
Randomization		X			
Physical Exam ^b	X				X ^c
Inclusion/Exclusion Criteria	X	X			
ECG (12-lead)	X				X
Vital Signs ^d	X	X	X	X	X
Hematology	X				X
Serum Chemistry	X				X

Pharmacogenomic sample	X				
Urine Pregnancy test, FOCP only		X			X
CGI-S	X	X			
CGI-I			X	X	X
C-SSRS	X	X	X	X	X
ADHD-RS-5	X	X	X	X	X
WFIRS-P, PSI-4-SF		X			X
Conners 3 ^e – parent, self		X			X
Concomitant Medication	X	X	X	X	X
Adverse Events		X ^f	X	X	X ^f
Drug Dispensed		X ^g	X	X	
Drug Return, Compliance			X	X	X
Optional PK Blood Sampling ^h			X	X	X

a To be obtained prior to performing any study procedures.

b Includes height and weight, excludes genitourinary system

c Changes from Screening only

d Seated (5 min) heart rate and blood pressure, temperature, respiratory rate

e Self report = 8-11 year olds only

f At Baseline, AEs are recorded only after SM is administered. Subjects with serious adverse events at EOS will be followed until the event has resolved or considered stable.

g Titration will begin after first dose of SM is administered

- ^h An optional PK substudy will take place between Visits 3 and 10, inclusive. Samples will be taken pre-dose and post-dose at Hours 1, 2, 4, and 6.
- ⁱ EOS or last visit in the case of early discontinuation.

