3.3 Procedures for Discontinuing Treatment and Removal of Subjects from Study

Subjects will be considered to have completed the study if they complete all visits up to and including Week 8 (EOS).

All subjects who discontinue early will complete the procedures listed for Week 8 (EOS).

All reasons for screening failure will be recorded. If the subject passes screening but fails eligibility at Baseline, the reason(s) will also be recorded.

The Investigator(s) or subjects themselves may stop SM treatment at any time for safety or personal reasons. A subject is free to withdraw from the study at any time for any reason without prejudice to their future medical care by the physician or at the institution. The Sponsor may also withdraw the subject at any time in the interest of subject safety. The withdrawal of a subject from the study should be discussed where possible with the Medical Monitor and/or Clinical Research Associate (CRA) before the subject stops SM. Subjects removed from the study for any reason will not be replaced.

Reasons for subject discontinuation may include:

- Withdrawal of consent
- Noncompliance
- Occurrence of unmanageable AEs
- Lost to follow-up
- Other

The primary reason for subject discontinuation must be recorded in the subject's medical record and on the eCRF. If a subject is withdrawn for more than one reason, each reason should be documented in the source document and the most medically significant reason should be entered on the eCRF.

If a subject misses doses of SM during this study, the Investigator shall counsel the subject/caregiver on the importance of compliance. If the subject has consistently missed doses, he or she may be discontinued from the study at the discretion of the Investigator and in consultation with the Medical Monitor; all procedures for discontinuation will be followed.

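### The compliance denominator is labelled planned doses but ends at the last dose taken, so the 80% limit cannot detect a child who stops drug and keeps attending visits

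*SAP*

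**What the plan says.** SAP 6.10 measures duration of exposure as "date of last dose minus date of first dose +1". It then defines percent compliance as capsules dispensed less capsules returned, divided by four times that same span. The next sentence drops any stretch with no returned capsules and, in doing so, says what the denominator is meant to be: "this period will also not be accounted for in the denominator (=number of planned doses". Compliance is summarised as below 80%, 80 to 120% and above 120%, by treatment period, in Table 14.1.2.5, together with exposure.

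SAP 6.5 lists major deviations. Item 4 is "Subject's treatment compliance < 80% or > 120" per cent. Item 2 is "Subjects who missed doses as per the treatment he was randomized to". The list is open and is to be finalised before database lock. SAP 6.3.4 limits the per-protocol set to ITT subjects who have "completed all 10 visits with no missing ADHD-RS-5 assessments and no major protocol violations".

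On follow-up, SAP 3.2 says that randomized subjects who took any study medication "will be followed according to the protocol regardless of the number of doses of SM taken, unless consent for follow-up is withdrawn". SAP 3.3 says that the investigator or the subject "may stop SM treatment at any time for safety or personal reasons".

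**The concern.** The label and the formula describe different quantities. Planned doses run to the end of the 8-week treatment phase (SAP 3.4.3), whereas the formula stops counting when the child does. It registers doses skipped between the first and the last dose, but not stopping altogether.

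This matters because SAP 3.2 and 3.3 together allow a child to stop drug and still attend all ten visits with every ADHD-RS-5 recorded. The per-protocol set is the only analysis population screened on adherence, and item 4 is its only numerical adherence criterion. At stake are the compliance summary and the supplementary per-protocol analyses of the primary and key secondary endpoints.

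**Working it through.** The SAP states no compliance result to reproduce, so the check evaluates its formula directly.

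**Inputs**
- Denominator: 4 × (last dose date − first dose date + 1), SAP 6.10.
- Limits: 80% and 120%, SAP 6.5 item 4.
- Planned treatment: 8 weeks, or 56 days, SAP 3.4.3; Visit 10 on Day 56 ± 2, SAP Table 1.
- Assumptions: four units a day in every arm, full intake up to the last dose on Day q, and all unused supply returned.

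**Formula as written.** 100 × 4q / (4 × q) = 100% for every q. The stopping day cancels. With 90% intake before stopping, the result is 90% for every q.

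**Against planned doses.** 100 × 4q / (4 × 56) = 100 × q / 56.

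| Last dose (Day) | SAP 6.10 formula | Share of 56 planned days |
|---|---|---|
| 14 | 100% | 25.0% |
| 21 | 100% | 37.5% |
| 28 | 100% | 50.0% |
| 35 | 100% | 62.5% |
| 42 | 100% | 75.0% |
| 44 | 100% | 78.6% |
| 45 | 100% | 80.4% |

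**By period.** Take the Day 28 stop with V5 on Day 21, and apply the formula to the dates within each period. Titration gives 21/21 = 100% on either basis. Maintenance gives 7/7 = 100% under the formula, against 7/35 = 20% of the planned days from Day 22 to Day 56.

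**Where the 80% line falls.** With 56 planned days, a stop on Day 44 or earlier is below 80%. The boundary moves with the Visit 10 window:
- 54 days: 43/54 = 79.6% and 44/54 = 81.5%, so the last failing day is 43.
- 55 days: 43/55 = 78.2% and 44/55 = 80.0%, so the last failing day is 43.
- 58 days: 46/58 = 79.3% and 47/58 = 81.0%, so the last failing day is 46.

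**Dependence on four units a day.** SAP 3.4.2 lists 2 × 100 mg for the 200 mg arm and does not mention filling up to four units. Without such filling the formula would return 50% in that arm, for example 2 × 21 / (4 × 21). The level changes, but the stopping day still cancels.

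**The case against.** The strongest objection concerns the per-protocol set. A reader might infer that children who are off drug at Week 8 enter it. The SAP does not support that. Item 2 of 6.5 makes missed doses a major deviation in its own right, and a child who takes nothing after Day 28 has missed doses on any plain reading. Having no threshold makes item 2 stricter, not weaker. What stands is narrower: item 4 does no work here, exclusion depends on item 2 alone, and the SAP does not say whether item 2 covers permanent stopping. If item 2 is applied literally, any missed dose already excludes, and the 80% limit adds nothing for under-dosing.

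Second, the route is narrow. SAP 3.3 largely treats stopping drug as leaving the study, with end-of-study procedures at that point. Those children fail the 10-visit condition. Only children who stop drug and keep attending under SAP 3.2 are concerned.

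Third, a reader might infer that the compliance table is simply wrong. Dividing by days up to the last dose is a legitimate measure of adherence while on treatment. The stop itself is visible in the same Table 14.1.2.5, where a Day 28 stop falls in the Day 24 to 30 exposure category. This objection largely stands: the fault is the label, and the use of this measure as a criterion that suggests it covers the whole planned course.

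Fourth, efficacy conclusions rest on the ITT population (SAP 6.13 and 6.14). The per-protocol analyses are supplementary. That stands too.

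**Conclusion.** The point holds as a minor one. The denominator in 6.10 does not match its own description, and compliance cannot fall when a child permanently stops drug but stays in the study. The 80% limit is therefore blind to such stopping: under the stated assumptions the formula returns 100% at any stopping day, against 50% of plan for a Day 28 stop.

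It would go too far to say that every stop by Day 44 is below 80% of plan. That is exact only for a 56-day span; the last failing day is 43 to 46 across the Visit 10 window. The number of children affected, and whether it differs by arm, cannot be estimated from the SAP. The primary analysis is unaffected.

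**What to change.** In 6.10, for subjects who attend the scheduled Visit 10, compute the denominator as 4 × (V10 date − first dose date + 1). Use matching limits by period, following the definitions in 6.2: first dose to V5 for titration, and after V5 to V10 for maintenance. Use this value in 6.5 item 4. Because 6.1 maps early termination visits to Visit 10 for summaries, state that V10 here means the scheduled visit.

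For early terminators, keep the span from first to last dose and label it compliance while on treatment. Keep last minus first dose plus 1 as the measure of duration of exposure. It would also help to state in 6.5 whether item 2 covers permanent stopping and how it relates to item 4.

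The cost is a few lines of wording and derivation, using dates already collected. Reported compliance becomes slightly less favourable, and some subjects may leave the per-protocol set. The new figure also combines staying on drug with daily intake, so a child whose drug was stopped by the investigator but who kept attending would count as below plan. A table footnote should say so.

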6.11 Site Pooling

This is a multicenter study. The primary analysis will be performed without site as a factor. However, for certain exploratory analyses small sites (defined as those with sample size <12 ITT subjects/site with uneven distribution of treatment groups) will be pooled to a group based on the geographic proximity. The purpose of pooling is to ensure that each site contains a sufficient number of subjects for statistical analyses that consider site as a factor.

6.12 Multiple Comparisons/Multiplicity

This is a 3-arm parallel group design. To account for the potential Type I error rate inflation due to multiple dose group comparisons to placebo, a sequential testing procedure with a fixed testing method will be used. The details of this multiplicity adjustment are defined in [Sections 6.13.1](#) and [6.14.1](#).

6.13 Efficacy Analyses

The efficacy analyses will be based on the ITT population and will be performed on ADHD-RS-5 total score, Conners 3-PS composite T score, Conners 3-SRS composite T score, WFIRS-P total score and PSI-4-SF total scores.

All confidence intervals, statistical tests, and resulting p-values will be reported as two-sided and will be assessed at the 5% significance level and interactions at 10%.

With respect to Analysis of Covariance, the Gamma regression will be used on the original scale, if the normality assumption for the standard ANCOVA model is not met based on diagnostic residual plots based on the data before imputation.

Multiplicity will be adjusted for the primary endpoint and key secondary endpoints.

The mean profiles of ADHD-RS-5 total score, Conners 3-PS composite T score, Conners 3-SRS composite T score, WFIRS-P total score, PSI-4-SF score and CGI-I score will be presented graphically by treatment group and scheduled study visit. In addition, plots of the Cumulative Distribution Functions of Change from Baseline in ADHD-RS-5 will be presented (Figures 14.2.1.1 - 14.2.6.2)

For supportive analysis, the absolute value and change from baseline to Week 8 (EOS) of all efficacy variables will be summarized using descriptive statistics by treatment group and visit (Tables 14.2.5.1- 14.2.5.6).

